Treatment Arms and Planned Duration for an Individual Subject:

Subjects will be randomly assigned to 1 of 2 dosing sequences; each sequence will have 4 periods. Subjects will be administered single doses of LY900014 U-200 formulation (on 2 occasions) and LY900014 U-100 formulation (on 2 occasions).

The study will include a 28-day screening period, followed by 4 study periods. There will be a wash-out period of at least 3 days between each study period. The follow-up visit will take place at least 14 days after the last dose.

Number of Subjects:

Up to 72 healthy men and women may be enrolled so that approximately 58 subjects complete the study.

Statistical Analysis:

Safety: Safety analyses will be conducted for all enrolled subjects who receive at least 1 dose of the study drug, whether or not they completed all protocol requirements. Safety assessments including, but not limited to vital signs, safety laboratory parameters, and adverse events will be captured and summarized using descriptive statistical methodologies.

Pharmacokinetics: Pharmacokinetic analyses will be conducted on data from all subjects receiving at least 1 dose of study drug and have evaluable PK data. Pharmacokinetic analyses will be conducted using standard noncompartmental method of analysis. Pharmacokinetic parameters will be assessed using free serum insulin lispro.

To compare PK parameters between LY900014 U-200 relative to LY900014 U-100, log-transformed AUC parameter estimates ($AUC_{[0-t_{last}]}$, $AUC_{[0-\infty]}$, and C_{max}) will be analyzed using a repeated measures, linear mixed-effects model where treatment, sequence, and period will be considered as fixed effects and subject as a random effect. From the model, the difference in least-square means (LSmeans) and the corresponding 2-sided 90% CIs for the treatment difference will be estimated and back transformed from the log scale to provide estimates of the ratio of geometric LSmeans and 90% CI for the ratio of the LSmeans. Bioequivalence will be concluded if the 2-sided 90% CI is completely contained within the interval (0.80, 1.25).

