10.3. Statistical Analyses

Statistical analysis of this study will be the responsibility of Lilly or its designee.

Pharmacokinetic/pharmacodynamic analyses will be conducted on data from all subjects who receive at least 1 dose of the study drug and have evaluable PK. Data from individual treatment periods may be excluded from the analysis for the following reasons:

- the clamp was terminated early (e.g., due to an AE, technical issues, or subject withdrawal),

- failure to administer full dose (e.g., appearance of liquid on the skin after withdrawing the needle) or
- failure to collect sufficient PK or GD samples in order to define key endpoints (e.g., C_{max} , R_{max}).

Primary statistical analyses will be conducted on the set of subjects who complete at least the first period of treatment with evaluable parameters. Supportive analyses may be done on the key parameters for the subjects who complete all treatment periods and have evaluable parameters. Safety analyses will be conducted for all enrolled subjects who receive at least 1 dose of the study drug whether or not they completed all protocol requirements.

Any change to the data analysis methods described in the protocol will require an amendment only if it changes a principal feature of the protocol. Any other change to the data analysis methods described in the protocol and the justification for making the change will be described in the study results.

Additional exploratory analyses of the data will be conducted as deemed appropriate. Study results may be pooled with the results of other studies for population PK analysis purposes to avoid issues with post hoc analyses and incomplete disclosures of analyses.

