10.3.2. Pharmacokinetic Analyses

10.3.2.1. Pharmacokinetic Parameter Estimation

Subjects who completed at least 1 period and had evaluable insulin lispro concentrations will be included in the PK analysis dataset. Pharmacokinetic analyses will be conducted using standard noncompartmental methods of analysis using [REDACTED] on a computer that meets or exceeds the minimum system requirements for these programs. The version of any software used for the analysis will be documented and the program will meet the Lilly requirements of software validation. It is possible that other validated equivalent PK software programs may be utilized if appropriate, warranted, and approved by global PK management.

Free serum insulin lispro concentrations will be used to calculate several PK parameters, including C_{max} , time of C_{max} (t_{max}), time to early half-maximal drug concentration (early 50% t_{max}), time to late half-maximal drug concentration (late 50% t_{max}), and $AUC_{(0-tlast)}$, AUC from time zero to 10 hours ($AUC_{[0-10h]}$), and $AUC_{(0-\infty)}$. The apparent total body clearance of drug calculated after extravascular administration (CL/F), half-life ($t_{1/2}$), apparent volume of distribution during the terminal phase after extra-vascular administration (V_z/F), may be determined. Other parameters may be calculated as deemed appropriate, such as partial AUCs.

Although attempts will be made to adhere to the scheduled collection times, it is recognized that situations arise that may compromise the scheduled times. Parameters will be individually calculated for each subject based on actual collection times and presented by summary statistics.

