10.3.2.2. Pharmacokinetic Statistical Inference

To compare PK parameters between LY900014 U-200 relative to LY900014 U-100, log-transformed AUC parameter estimates ($AUC_{[0-tlast]}$, $AUC_{[0-\infty]}$, and C_{max}) will be analyzed using a repeated measures, linear mixed-effects model where treatment, sequence, and period will be considered as fixed effects and subject as a random effect. From the model, the difference in LSmeans and the corresponding 2-sided 90% CIs for the treatment difference will be estimated and back-transformed from the log scale to provide estimates of the ratio of geometric LSmeans and 90% CI for the ratio of the LSmeans. Bioequivalence will be concluded if the 2-sided 90% CI is completely contained within the interval (0.80, 1.25).

$AUC_{(0-tlast)}$ and $AUC_{(0-\infty)}$ will also be analyzed using a linear fixed-effects model. The parameter estimates will be log-transformed before analysis. The model will include fixed effects for sequence, period, treatment, and subject nested within sequence. The LSmeans for each formulation, the difference in means between treatments, and the 90% CIs will be estimated from the model and back-transformed from the log scale to provide estimates of the geometric LSmeans, the ratio of the geometric LSmeans, and the 90% CIs. This analysis will only include completers.

A model with fixed effects for sequence, period, treatment, and subject nested within sequence without log transformation will be used for the analysis of the PK time parameters (early 50% t_{max} and t_{max}). The LSmeans, treatment differences in LSmeans, and the corresponding 90% CIs for the treatment differences will be estimated from the model. The treatment ratios and

90% CIs for the ratios will be calculated using Fieller's theorem. Other PK time parameters may be analyzed in a similar manner.

In addition, the analyses described above will also be performed on the population of subjects who completed and had evaluable PK data in all study periods.

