10.3.3. Pharmacodynamic Analyses

10.3.3.1. Pharmacodynamic Parameter Estimation

Glucodynamic assessments will be determined from the glucose clamp procedure, where the GIR over time will be used as a measure of insulin effect. Glucodynamic analyses will be conducted on those subjects who complete at least 1 clamp procedure.

A locally weighted scatterplot smoothing (LOESS) function will be applied to all individual GIR versus time profiles in each treatment group and/or period using CCI. The fitted data for each subject will be used to calculate the following GD parameters: time to onset of insulin action (t_{onset}), maximal GIR (R_{max}), time to R_{max} ($t_{R_{\text{max}}}$), time to half-maximal GIR before $t_{R_{\text{max}}}$ (early 50% $t_{R_{\text{max}}}$), time to half-maximal GIR after $t_{R_{\text{max}}}$ (late 50% $t_{R_{\text{max}}}$), total glucose infused over the duration of the clamp (G_{tot}). Additional partial glucose AUCs, such as G_{tot} over 30 minutes ($G_{\text{tot}0-30\text{min}}$), and G_{tot} over 1 hour ($G_{\text{tot}0-1\text{h}}$) may be computed as necessary. The values of these GD parameters will be summarized by treatment and/or period through descriptive statistics. Mean LOESS fits of GIR versus time profiles will be generated.

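### Section 10.3 ties the primary analysis set to an evaluable first period, whereas the rest of the protocol admits evaluable data from any period

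*Protocol*

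**What the plan says.** Section 10.3 contains two descriptions of who is analysed. It opens broadly: "Pharmacokinetic/pharmacodynamic analyses will be conducted on data from all subjects who receive at least 1 dose of the study drug and have evaluable PK". It then allows losses one period at a time: "Data from individual treatment periods may be excluded from the analysis for the following reasons", the reasons being an early end to the clamp, an incomplete dose, or too few samples to define a key endpoint. The following paragraph sets the primary population: "Primary statistical analyses will be conducted on the set of subjects who complete at least the first period of treatment with evaluable parameters".

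Two other places describe the PK population without a first-period condition:

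- Synopsis, Statistical Analysis, in the paragraph directly before the bioequivalence model: "Pharmacokinetic analyses will be conducted on data from all subjects receiving at least 1 dose of study drug and have evaluable PK data".
- Section 10.3.2.1: "Subjects who completed at least 1 period and had evaluable insulin lispro concentrations will be included in the PK analysis dataset".

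The primary model in Section 10.3.2.2 is a mixed model in which "treatment, sequence, and period will be considered as fixed effects and subject as a random effect". For glucodynamics, the synopsis and Section 10.3.3.1 ask only for one clamp: "Glucodynamic analyses will be conducted on those subjects who complete at least 1 clamp procedure". Section 10.2 is headed as the place for analysis populations, but it covers only disposition and subject characteristics and defines no set.

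**The concern.** Consider a subject whose Period 1 dose leaked and who then completes Periods 2 to 4 without fault. Under the primary-set sentence of Section 10.3 that subject is out. Under the opening of 10.3, the synopsis and 10.3.2.1 the subject is in and only Period 1 is dropped. The protocol gives no reason for a first-period condition, and the design supplies none. In both sequences Periods 2 to 4 contain each formulation at least once, so a within-subject comparison of U-200 with U-100 remains.

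Two things are at stake. The population for the confirmatory bioequivalence conclusion should be described in one way. In addition, the literal rule discards valid data, and the primary endpoint that would feel it is Cmax, which has much less power to spare than AUC.

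A smaller mismatch sits beside this. The opening of 10.3 makes the combined PK/PD analyses depend on evaluable PK, while the glucodynamic text asks only for a completed clamp.

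**Working it through.** **1. The definitions applied to one subject (Period 1 failed after dosing, Periods 2 to 4 valid)**

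| Source | Condition | Subject included? |
|---|---|---|
| 10.3, opening | at least 1 dose, evaluable PK | yes |
| Synopsis | at least 1 dose, evaluable PK | yes |
| 10.3.2.1 | at least 1 period completed, evaluable concentrations | yes |
| 10.3, primary-set sentence | first period completed, with evaluable parameters | no, read literally |

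The rescheduling and replacement rules do not remove the case. Rescheduling (Schedule of Activities note, Section 9.6) applies before dosing. Replacement applies to subjects who discontinue (5.2) or were never dosed (10.1). A subject with a post-dose failure in Period 1 who carries on meets neither condition.

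**2. Reproducing the stated power**

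Inputs from Section 10.1: 58 completers; log-scale SD of the within-subject difference 0.28 (AUC), 0.59 (Cmax), 0.57 (Gtot) and 0.64 (Rmax); limits 0.80 to 1.25; 90% CI, that is, two one-sided tests at 0.05. With two differences per subject, SE = SD/√(2 × 58).

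- Cmax: 0.59/√116 = 0.0548. Power is 84.4% at ratio 1.08 and 81.5% at 0.92 (stated: at least 80%).
- AUC: 0.28/√116 = 0.0260. Power is about 100% (stated: at least 95%).
- Gtot 94.9% and Rmax 89.7% at ratio 1.05 (stated: about 90%).

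The sample size statement reproduces and is not in question.

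**3. What a subject with Periods 2 to 4 contributes**

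The within-subject SD for Cmax is 0.59/√2 = 0.417. A complete subject has contrast variance σ²(1/2 + 1/2) = σ². With three periods it is σ²(1 + 1/2) = 1.5σ², so the subject keeps about 1/1.5 = two thirds of a complete subject's information. The first-period rule sets that to zero.

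Let m of the 58 subjects have only Period 1 failed. Then SE ≈ 0.417/√(58 − m) under the first-period rule and ≈ 0.417/√(58 − m/3) if they are kept. For m = 10 these give 0.417/√48 = 0.0602 and 0.417/√54.67 = 0.0564. The full mixed-model calculation gives 0.0602 and 0.0563 to 0.0564. Cmax power at ratio 1.08:

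| m (assumed) | First-period rule | Any-period rule |
|---|---|---|
| 2 | 83.3% | 84.1% |
| 4 | 82.1% | 83.7 to 83.8% |
| 6 | 80.8% | 83.3 to 83.4% |
| 10 | 77.9% | 82.5 to 82.7% |

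**4. Failures at random in any period**

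Assumptions: each period fails independently at a fixed rate, and the between-subject SD is 0.4. The SE is the generalised least squares SE for the two sequences, with treatment, sequence and period fixed and subject random. At 5%, 0.05 × 58 = 2.9 subjects have a failed Period 1, each with on average 3 × 0.95 = 2.85 good profiles. SE inflation is then 5.1% under the first-period rule and 3.3% under the any-period rule. Cmax power, first-period versus any-period rule:

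| Periods lost (assumed) | Ratio 1.08 | Ratio 0.92 | Cost of the rule |
|---|---|---|---|
| 2% | 83.2% vs 83.6% | 80.1% vs 80.6% | about 0.4 to 0.5 points |
| 5% | 81.1% vs 82.3% | 78.0% vs 79.3% | about 1.3 points |
| 10% | 77.4% vs 80.0% | 74.1% vs 76.8% | about 2.6 points |

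With a between-subject SD from 0.2 to 0.8, the cost runs from 1.2 to 1.3 points at 5% and from 2.5 to 2.8 points at 10%. AUC power stays at about 100% throughout.

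**The case against.** The strongest reply is that the sentence can be read in harmony with the rest. Periods are taken in order, so completing the first period may simply mean having completed at least one. Evaluability could then be handled period by period, as the same section allows, and nothing says outright that one excluded period deletes the subject. This may well be what was meant, or the phrase may be a slip for one period. It does not settle the text: the evaluability condition attaches most naturally to the first period, and a subject whose Period 1 clamp stopped early did not complete it on any reading.

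It can also be said that a narrower inference set within a wider PK dataset is legitimate. That is possible, but the protocol does not say so, and the synopsis places the wide set immediately before the bioequivalence model.

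On size, the reply is largely right. Most of the fall in power when periods are lost comes from the missing data themselves. At 5% loss and ratio 0.92 the any-period rule is also below 80%. The figures hold the sample at 58, while up to 72 may be enrolled and partial data from non-completers would add information. For glucodynamics, the specific text would ordinarily govern the general sentence, so that mismatch is secondary.

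A reader might infer that the primary set could be picked after the data are seen. The sponsor's study team is unblinded (7.3) and period exclusions are discretionary, but the documents do not support that inference. Only one sentence labels a primary set, and an SAP that is not shown may fix it.

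**Conclusion.** The point holds as an inconsistency in how the primary population is described. One sentence in Section 10.3 conflicts with three other statements in the protocol and, taken literally, discards valid within-subject comparisons that the primary model can use.

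The cost of the rule itself is about 1.3 points of Cmax power at 5% non-evaluable periods and a little over 2.5 points at 10%, with no effect on AUC. This rests on assumed failure rates, failures at random, 58 contributing subjects, and the SDs and ratios in Section 10.1.

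A reader might go further and infer bias, an inflated type I error, or an underpowered trial. None of these follows: random failures cost only precision, and the stated power reproduces. It should be fixed, but it is not a critical defect.

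**What to change.** In Section 10.3, replace the first-period condition with: *have at least 1 treatment period with the evaluable parameter being analysed*. State that only non-evaluable periods are excluded, and use the same wording in the synopsis and Section 10.3.2.1. As a secondary alignment, state in 10.3 that the glucodynamic set follows the synopsis and Section 10.3.3.1 (at least one completed clamp) and does not depend on evaluable PK.

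The cost is a short wording change, best made before analysis begins. It needs no new data, no change in sample size and no change to the model.

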10.3.1. Safety Analyses

10.3.1.1. Clinical Evaluation of Safety

All study drugs and protocol-procedure AEs will be listed; if the frequency of events allows, safety data will be summarized using descriptive methodology.

The incidence of symptoms for each treatment will be presented by severity and by association with study drug as perceived by the investigator. Symptoms reported to occur prior to study entry/enrollment will be distinguished from those reported as new or increased in severity during the study. Each symptom will be classified by the most suitable term from the Medical Dictionary for Regulatory Activities.

The number of study drug-related SAEs will be reported.

10.3.1.2. Statistical Evaluation of Safety

Safety parameters that will be assessed include safety laboratory parameters and vital signs. The parameters will be listed, and summarized using standard descriptive statistics. Additional analysis will be performed if warranted upon review of the data.

10.3.1.3. Statistical Evaluation of the Intensity of Injection Site Pain

Visual analog scale data for pain intensity, collected as described in Section 9.4.6.1, will be summarized using standard descriptive statistics and using the following categories of score: 0, 1 to 10, 11 to 20, 21 to 30, 31 to 40, etc., up to the maximum category by treatment.

10.3.2. Pharmacokinetic Analyses

10.3.2.1. Pharmacokinetic Parameter Estimation

Subjects who completed at least 1 period and had evaluable insulin lispro concentrations will be included in the PK analysis dataset. Pharmacokinetic analyses will be conducted using standard noncompartmental methods of analysis using [REDACTED] on a computer that meets or exceeds the minimum system requirements for these programs. The version of any software used for the analysis will be documented and the program will meet the Lilly requirements of software validation. It is possible that other validated equivalent PK software programs may be utilized if appropriate, warranted, and approved by global PK management.

Free serum insulin lispro concentrations will be used to calculate several PK parameters, including C_{max} , time of C_{max} (t_{max}), time to early half-maximal drug concentration (early 50% t_{max}), time to late half-maximal drug concentration (late 50% t_{max}), and $AUC_{(0-tlast)}$, AUC from time zero to 10 hours ($AUC_{[0-10h]}$), and $AUC_{(0-\infty)}$. The apparent total body clearance of drug calculated after extravascular administration (CL/F), half-life ($t_{1/2}$), apparent volume of distribution during the terminal phase after extra-vascular administration (V_z/F), may be determined. Other parameters may be calculated as deemed appropriate, such as partial AUCs.

Although attempts will be made to adhere to the scheduled collection times, it is recognized that situations arise that may compromise the scheduled times. Parameters will be individually calculated for each subject based on actual collection times and presented by summary statistics.

10.3.2.2. Pharmacokinetic Statistical Inference

To compare PK parameters between LY900014 U-200 relative to LY900014 U-100, log-transformed AUC parameter estimates ($AUC_{[0-tlast]}$, $AUC_{[0-\infty]}$, and C_{max}) will be analyzed using a repeated measures, linear mixed-effects model where treatment, sequence, and period will be considered as fixed effects and subject as a random effect. From the model, the difference in LSmeans and the corresponding 2-sided 90% CIs for the treatment difference will be estimated and back-transformed from the log scale to provide estimates of the ratio of geometric LSmeans and 90% CI for the ratio of the LSmeans. Bioequivalence will be concluded if the 2-sided 90% CI is completely contained within the interval (0.80, 1.25).

$AUC_{(0-tlast)}$ and $AUC_{(0-\infty)}$ will also be analyzed using a linear fixed-effects model. The parameter estimates will be log-transformed before analysis. The model will include fixed effects for sequence, period, treatment, and subject nested within sequence. The LSmeans for each formulation, the difference in means between treatments, and the 90% CIs will be estimated from the model and back-transformed from the log scale to provide estimates of the geometric LSmeans, the ratio of the geometric LSmeans, and the 90% CIs. This analysis will only include completers.

A model with fixed effects for sequence, period, treatment, and subject nested within sequence without log transformation will be used for the analysis of the PK time parameters (early 50% t_{max} and t_{max}). The LSmeans, treatment differences in LSmeans, and the corresponding 90% CIs for the treatment differences will be estimated from the model. The treatment ratios and

90% CIs for the ratios will be calculated using Fieller's theorem. Other PK time parameters may be analyzed in a similar manner.

In addition, the analyses described above will also be performed on the population of subjects who completed and had evaluable PK data in all study periods.

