5.1. Overall Design

This is a Phase 1, single-center, investigator- and subject-blind, 2-sequence, 4-period, randomized, replicated-crossover, 10-hour euglycemic clamp study in healthy subjects to compare the PK and GD of insulin lispro in LY900014 U-200 formulation versus insulin lispro in LY900014 U-100 after SC administration of 15 U insulin lispro dose. The treatments will be replicated such that each formulation is administered twice on different occasions to healthy subjects over 4 study periods.

Figure ITSS.1 illustrates the study design.

Abbreviation: CRU = clinical research unit.

*Single dose of LY900014 U-200 or LY900014 U-100 administered subcutaneously to the abdomen.

Figure ITSS.1. Illustration of study design for Protocol I8B-MC-ITSS.

Each subject will be administered LY900014 U-200 formulation (on 2 occasions) and LY900014 U-100 formulation (on 2 occasions). Subjects will be randomly assigned to 1 of the 2 dosing sequences (Table ITSS.2).

Table ITSS.2. Treatment Sequence Example for I8B-MC-ITSS

Treatment Sequence	Period 1	Period 2	Period 3	Period 4
1	LY900014 U-200	LY900014 U-100	LY900014 U-200	LY900014 U-100
2	LY900014 U-100	LY900014 U-200	LY900014 U-100	LY900014 U-200

Note: This is only an example table for illustration purpose; subjects will be assigned a treatment sequence according to the actual treatment randomization schedule provided to the unblinded site pharmacist.

Subjects will be required to attend the clinical research unit (CRU) on at least 6 occasions:

- 1 screening visit (may occur up to 28 days prior to randomization)
- 4 inpatient treatment visits for the clamp procedure (Periods 1 to 4) with a wash-out period of ≥ 3 days between discharge and the next admission to the CRU
- 1 follow-up visit (at least 14 days after the last dose).

Subjects will be admitted to the CRU on the evening before each dosing day and will remain in the CRU for the duration of the clamp period and until discharge by the investigator. Subjects are expected to fast for at least 8 hours before each dose. Following dose administration, each subject will undergo a euglycemic clamp procedure of up to 10 hours. Upon completion of the clamp procedures, the subjects will be provided a meal and observed overnight. Subjects will be discharged from the CRU the next day after medical assessments. Subjects may remain in the CRU if deemed necessary for safety monitoring, as determined by the investigator.

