10.1. Sample Size Determination

Up to 72 subjects may be enrolled so that approximately 58 subjects complete the study. Fifty-eight completing subjects in a replicated design will provide at least 95% power to show the 2-sided 90% CIs of the ratios of geometric least-squares means (LSmeans) for $AUC_{(0-\infty)}$, $AUC_{(0-t_{last})}$ between LY900014 U-200 and LY900014 U-100 to be within limits of 0.80 to 1.25. This calculation assumes a log-scale standard deviation for within-subject difference of 0.28 and up to a 5% difference in geometric LSmean ratio. There is also at least 80% power to show the 2-sided 90% CI of the ratio of the geometric means for C_{max} between the 2 formulations also within 0.80 to 1.25. This calculation assumes a log-scale standard deviation for within-subject difference of 0.59 and an 8% difference in geometric LSmean ratio for C_{max} with LY900014 U-200 compared to LY900014 U-100.

In addition, the study is adequately powered to evaluate the GD parameters. There is approximately 90% power to show the 2-sided 90% CI of the ratio of the geometric means between the 2 formulations for total amount of glucose infused (G_{tot}) and maximum GIR (R_{max}) are within 0.80 to 1.25. This calculation assumes a log-scale standard deviation for within-subject difference of 0.57 for G_{tot} and 0.64 for R_{max} and up to a 5% difference in the LSmean ratios.

Subjects who are randomized but not administered treatment may be replaced to ensure that approximately 58 subjects complete the study. The replacement subjects will assume the same treatment sequence as the subjects who dropped out and will complete that treatment sequence in its entirety.

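### The primary bioequivalence model, read literally, assumes no subject-by-formulation variance; if there is any, the deciding 90% CI is too narrow

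*Protocol*

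**What the plan says.** Protocol section 5.1 describes a 4-period design with two sequences, shown in Table ITSS.2 as alternating U-200 and U-100, in which "each formulation is administered twice on different occasions to healthy subjects over 4 study periods".

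Section 10.3.2.2 analyses the three log-transformed primary parameters with a model that it calls repeated measures and describes as a "linear mixed-effects model where treatment, sequence, and period will be considered as fixed effects and subject as a random effect". The decision rule follows: "Bioequivalence will be concluded if the 2-sided 90% CI is completely contained within the interval (0.80, 1.25").

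No subject-by-formulation term, random formulation effect or covariance structure is named anywhere. The supplementary AUC model has subject nested in sequence as a fixed effect and adds no such term; nor does the repeat analysis in completers. Section 10.3.3.2 uses the same mixed model for G_tot and R_max but gives no equivalence limits there.

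On size, section 10.1 states: "Fifty-eight completing subjects in a replicated design will provide at least 95% power" for AUC, with an SD of the within-subject difference of 0.28 and up to a 5% difference. For C_max it states at least 80% power: "This calculation assumes a log-scale standard deviation for within-subject difference of 0.59 and an 8% difference in geometric LSmean ratio".

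**The concern.** A model whose only random effect is subject treats a subject's four results as exchangeable once the fixed effects are removed. That holds only if every subject has the same true U-200 to U-100 ratio. If the ratio varies between subjects, giving each formulation twice does not average the variation away. It stays in the treatment estimate, while the pooled residual dilutes it.

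Replication creates the problem. In a crossover with one dose of each formulation, the residual contains the whole of sD². Here, two of the three within-subject contrasts compare a formulation with itself and carry none of it. The supplementary fixed-effects model pools its error in the same way, so it would not reveal the problem.

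At stake is the 5% risk, per parameter, of concluding bioequivalence when the true ratio lies on a limit. There is some reason not to build in sD = 0: the U-200 injection has half the volume (0.075 against 0.150 mL, Table ITSS.3) and a lower concentration of treprostinil (section 5.5), the excipient included to speed local absorption (section 3.2).

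**Working it through.** **Inputs.** From the protocol: n = 58 completers (10.1); two sequences of four periods (5.1), taken as 29 subjects each; SD of the within-subject difference 0.28 (AUC) and 0.59 (C_max); limits 0.80 and 1.25. The within-subject SD is sw = 0.28/√2 = 0.198 for AUC and 0.59/√2 = 0.417 for C_max. The documents do not give sD, so a range is assumed.

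**Step 1: reproduce the plan's power.** Two one-sided t-tests at 5% each, with SE = SD/√(2n) and 232 − 58 − 3 − 1 = 170 df, give:
- AUC: above 99.9% (stated: at least 95%).
- C_max: 84.4% at ratio 1.08 and 81.5% at 0.92 (stated: at least 80%).
- G_tot: 94 to 95%; R_max: 89 to 90% (stated: approximately 90%).

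The stated figures are reproduced. With SE = SD/√n, C_max power would be only 57% at 1.08 and 54% at 0.92. The plan therefore takes the full gain from replication, which matches sD = 0.

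**Step 2: what the model estimates.** A subject's mean log U-200 minus mean log U-100 has variance sw² + sD², so the treatment estimate has true variance (sw² + sD²)/n. Of the 170 residual df, 56 come from that contrast and 114 from the two same-formulation contrasts. The expected residual mean square is

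[56(sw² + sD²) + 114 sw²]/170 = sw² + 0.329 sD².

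Example, AUC with sD = 0.15: true SE = √[(0.0392 + 0.0225)/58] = 0.0326; model SE = √[(0.0392 + 0.329 × 0.0225)/58] = 0.0283; ratio 0.87. With t(0.95, 170) = 1.6539, the error at the limit is about Φ(−1.6539 × 0.869) = 7.5%.

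**Step 3: simulated error and coverage at a true ratio of 1.25.**

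| Parameter | sD (assumed) | Model SE / true SE | Error at 1.25 | 90% CI coverage |
|---|---|---|---|---|
| AUC | 0 | 1.00 | 5.0% | 90.0% |
| AUC | 0.05 | 0.98 | 5.4% | 89.3% |
| AUC | 0.10 | 0.93 | 6.3% | 87.4% |
| AUC | 0.15 | 0.87 | 7.6% | 84.8% |
| AUC | 0.20 | 0.81 | 9.0% | 81.9% |
| C_max | 0 | 1.00 | 5.0% | 90.0% |
| C_max | 0.05 | 0.995 | 5.1% | 89.9% |
| C_max | 0.10 | 0.98 | 5.3% | 89.4% |
| C_max | 0.15 | 0.96 | 5.7% | 88.6% |
| C_max | 0.20 | 0.94 | 6.2% | 87.6% |

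The normal approximation of Step 2 gives 5.3% (AUC) and 5.0% (C_max) at sD = 0.05. An analysis based on the per-subject contrast, with 56 df, holds about 5.0% in every row. In one simulated AUC data set with sD = 0.15, the random-intercept and fixed-subject models both gave an SE of 0.0269; random formulation effects gave 0.0304.

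**Step 4: C_max power if the planned 0.59 contains sD = 0.20.** Then 2sw² = 0.3481 − 0.04 = 0.3081 and sw² = 0.1541. The true SE is √[(0.1541 + 0.04)/58] = 0.0578. With 56 df, power is 77.1% at ratio 0.92 and 80.3% at 1.08.

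**The case against.** The strongest reply is that the protocol does not commit to a random-intercept model. It calls the model a repeated measures one and names no covariance structure. A statistical analysis plan could supply a structure that absorbs the interaction, and such detail is often left to that document. This stands as a limit on the point: it concerns the literal reading. But subject is the only random effect named, and a compound-symmetric structure would change nothing.

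Second, the harm depends on an sD that the documents do not give. This stands too. For AUC, sD = 0.20 exceeds the whole within-subject SD of 0.198 and would be about a third of the difference variance (0.04/0.1184), so the upper end of the range is demanding. Volume and treprostinil act on absorption, which makes variation more plausible for C_max, where the inflation is small. Section 3.2 reports similar total exposure for LY900014 and Humalog, and a pilot whose CIs met the limits. Those are results on averages: they neither estimate sD nor signal a problem.

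A reader might infer more, and the documents do not support it:
- **That the trial's error rate is inflated.** At sD = 0 the model is valid. The rates are also per parameter; if all three must pass, a false overall conclusion is rarer unless the other parameters lie well inside the limits.
- **That the stated C_max power is wrong.** It is reproduced. Section 10.1 gives no direction for the 8% difference, and even with sD = 0.20 inside the 0.59, power stays at 80% at ratio 1.08.
- **That false equivalence threatens G_tot and R_max.** Section 10.3.3.2 has no equivalence rule for them, so only CI coverage is affected.

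**Conclusion.** The point holds in conditional form. As literally written, the model behind the deciding CI assumes sD = 0 without saying so, and any positive sD makes its expected SE too small. The effect is clear for AUC only if sD is sizeable beside a within-subject SD of 0.198; for C_max it is modest throughout the assumed range. The figures rest on 58 complete subjects, 29 per sequence, the planned SDs and assumed values of sD. Nothing in the protocol is contradicted or miscalculated. This is a change that should be made because it protects the primary decision cheaply; it is not a fault that invalidates the plan.

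**What to change.** - **10.3.2.2 and the synopsis:** specify correlated random formulation effects per subject (or a random subject-by-formulation term), with Satterthwaite or Kenward-Roger df, fitted to all subjects in the primary set.
- **Non-convergence:** name in advance a simpler structure that keeps the subject-by-formulation term. Use the per-subject contrast (mean log U-200 minus mean log U-100) only as a completer sensitivity analysis. Section 10.3 keeps in the primary set subjects who complete at least the first period; the contrast would drop those with only one formulation and misweight those with two or three periods.
- **10.3.3.2:** use the same model, for CI coverage only.
- **10.1:** state that the C_max power assumes no subject-by-formulation variance, and give the figures from Step 4 or similar.

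The cost is wording and one model statement. Error df fall from about 170 to 56, and the CI widens by about 1% (1.6725/1.6539 = 1.011). When sD = 0, C_max power at ratio 0.92 falls from 81.5% to about 81%. The wording should be settled before unblinded analysis, because a model chosen afterwards would be open to challenge.
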